8.5 Pharmacokinetics

In all participants enrolled, sparse pharmacokinetic samples will be collected for determination of regorafenib and its metabolites M-2 and M-5 (in plasma) and nivolumab (in serum) as specified in Table 1–4.

Deviations from planned sampling time intervals will not be considered as protocol deviations. However, omission of samples other than specified in the PK sampling Table 1–4 will be considered a protocol deviation. The date and clock time of each sample as well as dates and times of the regorafenib administration and start and stop times of nivolumab infusion will be recorded in the eCRF as PK estimates will be based on the sampling times relative to dosing times.

For regorafenib, meal intake time should be collected on PK sampling days together with the dosing time.

Samples may be collected irrespective of any dose modifications during the treatment cycle. If regorafenib is not administered on the day of PK sampling, the pre-dose samples will be collected, the post-dose samples will not be collected. Pre-dose samples will also not be collected if participants have not taken regorafenib on the previous day. However, if regorafenib is re-started than PK sampling should resume as scheduled. Pre-dose samples will also not be collected if participants have not taken regorafenib on the previous day. However, if regorafenib is re-started than PK sampling should resume as scheduled. Pre-dose samples will also not be collected if participants have not taken regorafenib on the previous day. However, if regorafenib is re-started than PK sampling should resume as scheduled.

The regorafenib dose that separates the pre- and post-dose sample needs to be taken under supervision and the time of dosing should be recorded.

Regorafenib data from this study will be pooled with data from other clinical studies for pharmacometric analysis. The nivolumab serum concentration may be analyzed using a previously developed population PK model to determine measures of individual exposure.

Model determined exposures of regorafenib and/or nivolumab may be used for exposure response analyses of selected measures of efficacy, safety or biomarker changes. The results of population PK and exposure response analyses will be reported separately from the overall study results.

The PK analysis will be performed using validated analytical methods. Exploratory measurements of other moieties may be performed, if needed.

Instructions for the collection, processing, storage and shipment of PK samples will be provided separately by the sponsor (e.g., sample handling sheets or laboratory manual).

8.6 Pharmacodynamics

Pharmacodynamic biomarkers will be evaluated in this study and are described in Section 8.8.

8.7 Genetics

Pharmacogenetic analyses except whole genome sequencing will be part of the biomarker investigations in this study. See Section 8.8 for details.

8.8 Biomarkers

Biomarker investigations in the current study will include pharmacodynamic biomarker assessments and assessments of biomarkers that may associate with efficacy and/or safety.

Both genetic as well as non-genetic biomarkers will be investigated. Genetic investigations may be of any kind (including whole exome sequencing and RNA sequencing), except for whole genome sequencing.

All biomarker analyses are covered by the main study informed consent. No separate consent is required as no whole genome sequencing will be performed. The investigator will assess if tumor specimen acquisition is medically feasible.

Timing:

The following samples for biomarker research are required and will be collected from all participants as specified in the SoA (Table 1–2) and schedule of Biomarker Blood Sampling (Table 1–3).

For details regarding tumor tissue collection please refer to the below specification:

At screening:

- Archival tumour tissue sample is mandatory if available for all cohorts.
 - HNSCC IO treated cohort: the archival tissue shall be preferably before IO treatment if available.

AND

- Provision of recent tumor tissues (defined as an archival biopsy not older than 180 day and after last anti-tumor treatment; or a new biopsy) are
 - o mandatory for all participants in HNSCC (IO treated) in Stage 1 and 2
 - mandatory for HNSCC (IO naïve) in Stage 2
 - mandatory if medically feasible (as judged by the Investigator) for all participants in the ESCC, PDAC, and BTC cohorts and for participants in Stage 1 of the HNSCC (IO naïve) cohort.
 - Optional for GBM/AA cohort and should only be considered if tumor is accessible and biopsy is deemed safe by the Investigator

C2D8 (+7 days):

- In Stage 1: mandatory if medically feasible (as judged by the Investigator) for all participants in HNSCC (IO treated); optional for all other cohorts
- In Stage 2: mandatory if medically feasible (as judged by the Investigator) for all participants in all cohorts except the GBM/AA cohort. For the GBM/AA cohort, tumor tissue collection is optional and should only be considered if tumor is accessible and biopsy is deemed safe by the Investigator.

EoT:

• Optional for all cohorts.

Page 78 of 135

	HNSCC IO Naïve	HNSCC IO naïve	HNSCC IO treated	ESCC	PDAC	BTC	GBM/AA
	Stage 1	Stage 2	Stage 1+2	Stage 1+2	Stage 1+2	Stage 1+2	Stage 1+2
Archival	Mandatory	Mandatory	Mandatory	Mandatory	Mandatory	Mandatory	Mandatory
tumor tissue	if available	if available	if available, preferably before IO treatment	if available	if available	if available	if available
Recent	Mandatory	Mandatory	Mandatory	Mandatory	Mandatory	Mandatory	Optional
tumor tissuesª	if medically feasible			if medically feasible	if medically feasible	if medically feasible	
C2D8 Stage 1 participants	Optional	NA	Mandatory if medically feasible	Optional	Optional	Optional	Optional
C2D8	NA	Mandatory	Mandatory	Mandatory	Mandatory	Mandatory	Optional
Stage 2		if medically	if medically	if medically	if medically	if medically	
participants		feasible	feasible	feasible	feasible	feasible	
EoT	Optional	Optional	Optional	Optional	Optional	Optional	Optional

 Table 8–2
 Requirements for Tumor Tissue Collection

Abbreviations: AA= Anaplastic astrocytoma; BTC = Biliary Tract Carcinoma; C = Cycle; D = Day; EoT = End of treatment; ESCC = Esophageal squamous cell carcinoma, HNSCC = Head and neck squamous cell cancer; IO = Immune oncology; NA = not applicable; PDAC= Pancreatic ductal adenocarcinoma

a) archival biopsy not older than 180 day and after last anti-tumor treatment; or a new biopsy Note: Medically feasible as judged by the Investigator

Additional samples may be collected at additional time points during the study if warranted and agreed upon between the investigator and the sponsor. Sampling time points might also be moved or removed.

Medical history information – if any additional molecular information about the tumor was collected in the course of treatment prior to entry of the participant in the study, the results may be collected in order to include this data in biomarker analyses.

Sample handling and storage:

Tumor tissue requirement for archival tissue: Formalin-fixed paraffin-embedded block or minimum of 20 slides if available. Less slides are acceptable if provision of a block or 20 slides is not feasible.

Tumor tissue requirement for recent tissue at baseline, C2D8 and EoT tissue: Formalin-fixed paraffin-embedded block or minimum of 20 slides, obtained from core needle biopsy, punch biopsy, excisional biopsy or surgical specimen. Fine needle aspirates or other cytology samples are not acceptable.

Details on the collection, processing, shipment and storage of samples will be provided in separate documents (e.g., sample handling sheets or lab manual). Samples may be stored for a maximum of 15 years (or according to local regulations) following the end of the study at a facility selected by the sponsor to enable further analyses.

Reporting:

Some of the results of biomarker investigations may be reported separately (e.g., in a biomarker evaluation report).

8.8.1 Pharmacodynamics Biomarker

Pharmacodynamics biomarker will be evaluated in samples collected before and during treatment to investigate the impact of regorafenib and nivolumab on these biomarkers and may be correlated with safety and/or efficacy. Tissue-based pharmacodynamics biomarker evaluations will be conducted in available paired tumor biopsies (recent tumor tissues at screening and on-treatment/EoT tumor biopsy).

Candidate pharmacodynamics biomarkers may include (but are not limited to):

- Intra-tumor PD biomarkers such as immune cell infiltrations (e.g. effector T cells [T_{eff}], T_{reg}, marcophages), expression of immune genes/signatures, and/or parameters in the regorafenib targeted pathways in paired tumor biopsies (pre- and on-treatment)
- Quantification and characterization of immune cell populations in blood (e.g. T cells, Myeloid-Derived Suppressor Cells [MDSC], etc.) analyzed e.g., by flow-cytometry
- Systemic levels of immune mediators (e.g., cytokines, chemokines) from serum or plasma and tumor markers from circulating tumor deoxyribonucleic acid (ctDNA)
- Plasma proteins of interest for regorafenib (e.g., TIE-1, sVEGFR1, sVEGFR2, VEGF, angiopoietin 1 [Ang1])
- Circulating miRNA
- Composition of gut microbiome by e.g., bacterial taxonomy profiling in stool sample

8.8.2 Biomarkers that may associate with Response

Baseline candidate biomarkers will be evaluated for correlation with the response to treatment (to identify possible "predictive biomarkers"). Samples from tumor materials, blood and stool will retrospectively be analyzed.

Candidate biomarkers from baseline samples that may associate with response may include (but are not limited to):

- Tumor immune status (e.g., PD-L1 expression, immune gene expression profiles, immune cell infiltration e.g. T_{eff}, T_{reg}, macrophages) at baseline
- Expression of parameters of interest for regorafenib (e.g., ligands of targeted receptor tyrosine kinases) in baseline tumor materials
- Baseline TMB/ tumor mutations (e.g. B2M, JAK1/2/3) as detected in tumor and/or ctDNA
- Baseline immune cell populations in blood and baseline systemic levels of immune mediators (e.g., cytokines/chemokines)
- Germline genetic variants in genes of interest (e.g., cc-chemokine ligands CCL4 and CCL3, cc-chemokine receptor 5 (CCR5))
- Baseline circulating miRNA markers
- MGMT methylation status and IDH mutation status (GBM/AA only)
- HPV/p16 (oropharyngeal HNSCC only)
- Baseline composition of gut microbiome by e.g., bacterial taxonomy profiling in stool sample

8.8.3 Other Biomarkers

In addition to the biomarkers described above, further biomarkers related to the mode of action or the safety of regorafenib and nivolumab and similar drugs may be examined. The same applies to further biomarkers deemed relevant to cancer and associated health problems. These investigations may include e.g., diagnostic testing, potentially predictive, safety, pharmacodynamics or monitoring biomarkers.

8.9 Immunogenicity Assessments

Blood (serum) samples will be collected from all participants treated with nivolumab for analysis of anti-drug-antibodies (ADAs) and neutralizing antibodies (NABs) in Cycles 1, 2, 5 and 19, pre-infusion (Table 1–4).

Serum samples will be screened for ADAs and the titer of confirmed positive samples will be reported. Other analyses may be performed to verify the stability of ADAs and/or further characterize the immunogenicity of nivolumab.

The detection and characterization of ADAs will be performed using a validated assay method. ADAs may be further characterized and/or evaluated for their ability to neutralize the activity of nivolumab.

Instructions for the collection, processing, storage and shipment of immunogenicity samples will be provided separately by the Sponsor (e.g., sample handling sheets or laboratory manual).

9. Statistical Considerations

This is a single arm, open-label Phase 2 study with ORR per RECIST1.1 per local assessment for all solid tumors except GBM/AA or RANO per local assessment for GBM/AA as primary endpoint.

Each cohort will be examined in 2 stages based on a Sargent 3-outcome design (Sargent et al. 2001) with one-sided alpha of 0.1 (false positive rate), beta (false negative rate) of 0.1, power of 70% and likelihood of futility of 70% when the null hypothesis is true. At the end of Stage 2, 3 outcomes are possible based on 2 efficacy boundaries. The first outcome is considered negative if there is an insufficient number of responders to pass the pre-defined low boundary for efficacy. The second outcome is considered a positive outcome if the number of responders meets or surpasses the pre-defined target boundary for efficacy. The third outcome is a result in which the number of responders lies between the two boundaries and is considered inconclusive for declaring a positive outcome based on the pre-defined target.

If Stage 1 does not show the targeted level of activity after 2 tumor assessments, recruitment into Stage 2 may be discontinued. In addition, the totality of the data, including the duration and depth of response and overall risk-benefit assessment may be considered in the decision to terminate or continue the expansion after Stage 1. The complete cohort of participants from Stage 1 and Stage 2 will be tested at the one-sided alpha of 0.1. A one-sided exact binomial test will be conducted to test the hypotheses.

All participants treated will be included in the evaluation of response rate, not treated participants will be replaced. Any treated participant who does not qualify as a responder according to the tumor assessment criteria will be considered as non-responder.

9.1 Statistical Hypotheses

The underlying hypotheses to be tested in this study are

HNSCC (IO naïve): H0: $ORR_{Combination} \le 15\%$ versus H1: $ORR_{Combination} \ge 30\%$

HNSCC (IO treated): H0: $ORR_{Combination} \leq 5\%$ versus H1: $ORR_{Combination} \geq 19\%$

ESCC: H0: $ORR_{Combination} \le 15\%$ versus H1: $ORR_{Combination} \ge 30\%$

PDAC: H0: $ORR_{Combination} \le 10\%$ versus H1: $ORR_{Combination} \ge 20\%$

BTC: H0: $ORR_{Combination} \le 10\%$ versus H1: $ORR_{Combination} \ge 20\%$

GBM/AA: H0: $ORR_{Combination} \le 15\%$ versus H1: $ORR_{Combination} \ge 30\%$

9.2 Sample Size Determination

Cohort: HNSCC (IO naïve), ESCC and GBM/AA

In Stage 1, a total of 9 participants should be targeted for each cohort. To target 30% of ORR at least 1 responder out of the 9 participants is needed per cohort.

In Stage 2, per cohort, 21 additional participants should be added in order to target 30 participants. If 8 or more out of the 30 participants respond, the cohort is considered as showing a positive outcome. If 5 or less out of the 30 participants respond, the cohort is considered as showing a negative outcome. If 6 or 7 participants respond, outcome is inconclusive.

Cohort: HNSCC (IO treated)

In Stage 1, a total of 14 participants should be targeted in the cohort. To target 19% of ORR at least 1 responder out of the 14 participants is needed.

In Stage 2, 6 additional participants should be added in order to target 20 participants. If 3 or more out of the 20 participants respond, the cohort is considered as showing a positive outcome. If 1 or less out of the 20 participants respond, the cohort is considered as showing a negative outcome. If 2 participants respond, outcome is inconclusive.

Cohort: PDAC and BTC

In Stage 1, a total of 17 participants should be targeted in the cohort. To target 20% of ORR at least 1 responder out of the 17 participants is needed.

In Stage 2, 28 additional participants should be added in order to target 45 participants. If 8 or more out of the 45 participants respond, the cohort is considered as showing a positive outcome. If 5 or less out of the 45 participants respond, the cohort is considered as showing a negative outcome. If 6 or 7 participants respond, outcome is inconclusive.

9.3 **Populations for Analyses**

The following populations are defined:

Table 9–1 Populations for Analyses

Population	Description
Enrolled	All participants who sign the ICF
FAS (full analysis set)	All participants who have received any dose of study intervention
SAF (safety analysis set)	All participants who have received any dose of study intervention
r-PKS	All patients who have received at least 1 dose of regorafenib and with at least 1 valid regorafenib concentration after dosing and no protocol deviations affecting the validity of the regorafenib PK will be included in the regorafenib PK analysis set.
n-PKS	All patients who have received at least 1 dose of nivolumab and with at least 1 valid nivolumab concentration after dosing and no protocol deviations affecting the validity of the nivolumab PK will be included in the nivolumab PK analysis set.
IMS	All patients who have received at least one dose of nivolumab and have at least one ADA sample taken (at baseline and during the treatment or FU observation period) that is appropriate for ADA testing (with reportable result) will be included in the analysis set for the immunogenicity analysis of nivolumab, which is defined as the immunogenicity analysis set.

Abbreviations: ADA = Anti-drug antibodies; FAS = Full analyses set; FU = Follow-up; ICF = Informed consent form; IMS = Immunogenicity analysis set; PK = Pharmacokinetics; n-PKS = Nivolumab PK analysis set; r-PKS = Regorafenib PK analysis set; SAF = Safety analysis set

As the safety analysis set (SAF) equals the full analysis set (FAS), all analyses related to safety will be performed on the Full Analysis Set.

9.4 Statistical Analyses

Analysis will be performed using SAS (SAS Institute, Cary, North Carolina, USA), Version 9.2 or higher. The specific version used will be mentioned in the statistical analysis plan (SAP).

The statistical analysis plan will include a more technical and detailed description of the statistical analyses described in this section. This section is a summary of the planned statistical analyses of the most important endpoints including primary and secondary endpoints.

9.4.1 General Considerations

All analyses will be conducted at one-sided type-I error level of 10% or two-sided type-I error level of 20% respectively. A one-sided exact binomial test will be conducted in the Stage 2 to test the primary endpoint. Confidence intervals will be presented for selected variables.

27 JAN 2021

9.4.2 **Primary Endpoint(s)**

The primary endpoint of the study is ORR defined as the proportion of participants with best overall response of confirmed CR or partial response (PR). ORR is based on RECIST 1.1. for all solid tumors by local assessment and for the GBM/AA cohort ORR is based on RANO by local assessment. Participants for whom best overall tumor response is not CR or PR, as well as participants without any post-baseline tumor assessment will be considered non-responders.

The primary endpoint is ORR based on RECIST 1.1 or RANO as assessed by the investigator. The primary efficacy variable will be analyzed per cohort. The primary analysis will be done on the Full Analysis Set.

Methods used will include frequency tables (with the ORR table also including all "Best overall response" categories) as well as 80% two-sided Clopper-Pearson confidence intervals and the results of an exact binomial test.

9.4.3 Secondary Endpoint(s)

The secondary efficacy endpoints in this study are Duration of Response (DOR), Disease Control Rate (DCR), PFS, 6 month PFS, according to RECIST 1.1 or RANO and additionally OS and 1 year OS in the Stage 2.

DOR (for PR and CR) is defined as the time (in days) from the first documented objective response of PR or CR, whichever is noted earlier, to first documented objective disease progression or death (if death occurs before progression is documented). DOR will be defined for responders only, i.e. participants with a CR or PR. The actual dates the tumor scans were performed will be used for this calculation. DOR for participants who have not progressed or died at the time of analysis will be censored at the date of their last tumor evaluation.

PFS is defined as the time (in days) from start of study intervention to the date of first objectively documented PD or death from any cause (if no progression is documented). The actual date of tumor assessments will be used for this calculation. PFS for participants without PD or death at the time of analysis will be censored at the date of their last tumor evaluation. PFS for participants who have neither tumor assessments nor death after baseline will be censored at Day 1.

OS is defined as the time (in days) from start of study intervention to the date of death due to any cause. If a participant is not known to have died, then OS will be censored at the date of last known date participant alive. If a participant is lost to FU before any assessment after assignment to study intervention, this participant will be censored at Day 1.

Safety is also considered as secondary endpoint. For details please refers to Section 9.4.5.

The secondary efficacy endpoints will be based on investigator assessments. Analyses will be done on the Full Analysis Set per cohort.

For analyses of the secondary endpoints, proportion-based efficacy variables will be using frequency tables as well as 80% two-sided Clopper-Pearson confidence intervals. With regard to time to event data, these will be summarized descriptively using Kaplan Meier methodology and plots, as well as median estimates based on Greenwood's formula, including 80% two-sided confidence interval

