For participants who discontinue study treatment without confirmed radiological disease progression every effort should be made to continue tumor evaluations (by computed tomography [CT]/magnetic resonance imaging [MRI]) until confirmation of radiological progression per RECIST 1.1 or RANO and/or start of first subsequent systemic anti-cancer treatment whichever comes first, or any other criterion for withdrawal is met. During the efficacy FU visits, CT/MRI evaluations will be performed every 12 weeks (+/-14 days). Following the occurrence of progression per RECIST 1.1 or RANO during efficacy FU, scans for tumor assessments may be obtained to confirm progression as per iRECIST or iRANO as detailed in Section 8.1. For GBM/AA tumor assessment per RANO will also include use of corticosteroids and neurological status. In addition, study intervention-related toxicity/AE and first subsequent anti-cancer therapy will be followed up until completion of the active FU. Active FU will either be terminated by the last safety FU visit or thereafter by the last tumor assessment or documentation of first subsequent systemic anti-cancer treatment or any criterion for withdrawal is met.

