7.1 Discontinuation of Study Intervention

Withdrawal from study treatment period

Patients **MUST** be withdrawn from both, regorafenib and nivolumab, if any of the following occurs:

- At their own request. At any time during the study and without giving reasons, a patient may decline to participate further. The patient will not suffer any disadvantage as a result.
- If, in the investigator's opinion, continuation of the study treatment would be harmful to the patient's well-being.
- Confirmed PD as per iRECIST or iRANO criteria; however, treatment may be continued provided that the patient derives ongoing clinical benefit as determined by the treating physician (Participants who complete 24 infusions of nivolumab [after approximately 2 years of treatment] need to discontinue nivolumab treatment. Regorafenib monotherapy treatment can be continued beyond 2 years until discontinuation criteria are met).
- Clinical progression (every effort should be made to obtain radiological confirmation of PD during active FU). Note: In cases where radiographic evaluation is not possible, clinical progression may be used. Clinical progression is based on the judgment of the investigator (e.g., defined as worsening of the ECOG PS ≥3 or symptomatic deterioration including increase in liver function tests).
- The development of a second primary malignancy that requires a different treatment.
- Development of any intercurrent illness or situation which may, in the judgment of the investigator, affect assessments of clinical status and study endpoints to a relevant degree.
- Severe allergic reactions, such as exfoliate erythroderma, anaphylaxis, or vascular collapse.
- Start of subsequent systemic anti-cancer treatment.
- Substantial non-compliance with the requirements of the study.
- If all study drugs (regorafenib and nivolumab) have to be permanently discontinued. Requirements for discontinuation of individual study drugs are described in Section 6.6.1 for regorafenib and in Section 6.6.2 for nivolumab.
- Use of illicit drugs or other substances that may, in the opinion of the investigator or their designated associate(s), have a reasonable chance of contributing to toxicity or otherwise confound the results.
- Pregnancy
- Participant lost to FU
- Death
- Withdrawal of regorafenib only:

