27 JAN 2021

For consistency, the same imaging modality and equivalent technique (e.g. slice thickness, field of view, contrast agent, bone scan radiotracer, magnet strength) should be used for all scans across all time points (including baseline scans) performed on an individual participant.

Imaging time-points:

The time-points for CT, MRI and bone scans, if applicable, are described in the SoA (Section 1.3). Baseline radiological tumor assessments will be conducted within 28 days before C1D1.

Scans performed prior to the participant signing informed consent may be used for baseline tumor assessments provided:

- CT/MRI scans were conducted within 28 days of C1D1
- Bone scans were conducted within 42 days of C1D1
- There has been no intervening therapy between the scans and C1D1
- The scans meet the imaging requirements of this protocol (Section 8.1)

Tumor assessments during the treatment period will occur every 8 weeks (\pm 7 days) through Cycle 8 (or until treatment discontinuation, if treatment discontinuation occurs before) and every 12 weeks (\pm 14 days) thereafter during the treatment period until initial criteria for disease progression are met. When disease progression occurs, tumor assessments should follow the iRECIST (Section 10.6.2) or iRANO timing (Section 10.6.4) as described below.

Tumor assessment will be repeated at the EoT visit or safety follow-up visit if not performed within 12 weeks since the most recent tumor assessment. For participants who discontinue study treatment without radiological disease progression, every effort should be made to perform CT/MRI tumor assessments every 12 weeks (\pm 14 days) during active-FU until radiological progression of the disease occurs or the start of a new anti-cancer treatment. The schedule of tumor assessments beyond unconfirmed progression per RECIST 1.1 or RANO during the active FU is described below.

Tumor response assessments for all participants except those with GBM/AA:

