5.3.2 Main Analytical Approach

ORR will be displayed using frequency counts and percentages as well as 80% two-sided Clopper-Pearson confidence intervals, by cohort.

Summary statistics will be displayed for all best response categories: CR, PR, stable disease (SD), progression disease (PD) by radiographic imaging and PD by clinical judgment. Frequency counts and percentages with 80% two-sided Clopper-Pearson CI will be displayed.

Version 3.0 Page: 5 of 9

Following analyses will be created per cohort:

- -Swimmer plot of overall response and waterfall diagram of best overall response with maximum percentage reduction in target lesion from baseline up to the time of the first progression per RECIST 1.1 for solid tumors cohorts and per RANO for GBM/AA cohort.
- -Change in sum of target lesions from baseline per RECIST1.1 over time by individual participants for solid tumor cohorts (except GBM/AA cohort) presented by a spider plot.
- -Change in the sum of products of perpendicular diameters of target lesions from baseline over time per RANO by individual participants for GBM/AA cohort presented by a spider plot.

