5.4.1.3 Sensitivity Analyses

No sensitivity analysis is planned.

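### In the five RECIST cohorts, clinical progression without a later scan is not a PFS event, which biases PFS and 6-month PFS upward; a sensitivity analysis should show by how much

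*Protocol*

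**What the plan says.** Protocol 9.4.3 runs PFS from start of study intervention to "the date of first objectively documented PD or death from any cause (if no progression is documented". It uses the actual dates of tumor assessments. Everyone else falls under one rule: "PFS for participants without PD or death at the time of analysis will be censored at the date of their last tumor evaluation". Participants with neither a post-baseline assessment nor a death are censored at Day 1. The section has no rule for clinical progression, new therapy or missed scans.

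Protocol 7.1 makes clinical progression a reason to withdraw both drugs. It asks for radiological confirmation in active follow-up and then adds: "In cases where radiographic evaluation is not possible, clinical progression may be used". It does not say whether that use extends to the endpoints. Protocol 10.6.1 has RECIST participants who deteriorate without objective progression reported as symptomatic deterioration, not as PD.

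After treatment stops, scans continue only until confirmed radiological progression or "start of first subsequent systemic anti-cancer treatment whichever comes first" (Protocol 4.1.3; Protocol 8.1 has a similar stopping rule, "until radiological progression of the disease occurs or the start of a new anti-cancer treatment"). Survival follow-up continues every 3 months (Protocol 4.1.4).

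SAP v3.0, Section 5.3.2, lists among the best-response categories "progression disease (PD) by radiographic imaging and PD by clinical judgment". SAP 5.4.1.3 states: "No sensitivity analysis is planned". SAP 5.4.1.1 and 5.4.1.2 refer the PFS definition to SAP v2.0 and the analysis to what was done at primary completion. SAP v2.0 is not among the documents.

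**The concern.** Take a PDAC participant who declines at month 3, cannot be scanned, and dies at month 8. The response table can show clinically judged progression. The PFS curve shows the same participant progression-free at 6 months, with an event at month 8. If alive at the cut-off, this participant is censored at the last scan before the decline and leaves the risk set just when progression has happened. Kaplan-Meier assumes that those censored have the same outlook as those who remain, and here they do not.

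PFS and 6-month PFS are named secondary endpoints in a single-arm trial, so they can be read only against outside values such as those in Protocol 2.2. An upward shift of a few points in 6-month PFS could be mistaken for activity.

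**Working it through.** **The plan's own figure.** There is none to reproduce. No target, event count or power is stated for PFS or 6-month PFS.

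**Inputs from the documents**
- Event and censoring rules: Protocol 9.4.3.
- Scans every 8 weeks through Cycle 8: Protocol 8.1. Week 32 lies beyond 6 months, so the later 12-week interval hardly affects the 6-month figure and was not modelled.
- Minimum follow-up about 10 months: Protocol 4.4. Follow-up was drawn uniformly from 10 to 20 months; the upper end is assumed.
- Median to progression 3.7 months: the PFS of two BTC studies in Protocol 2.2, used as an illustration.
- Median post-progression survival: the same two studies report OS of 5.4 and 14.2 months. The differences are 5.4 − 3.7 = 1.7 and 14.2 − 3.7 = 10.5 months. A difference of medians is only a rough guide, so the range taken is 1.7 to 10 months.

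**Assumption without a source.** The share of progressions that are clinical only, with no later scan, is c = 10, 20 or 30%. I read 6-month PFS as a Kaplan-Meier estimate.

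**Closed-form check.** Let T be time to progression and D time to death, both with exponential components. An affected participant should have an event at T but has one at D, so

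excess at 6 months ≈ c × [P(D > 6) − P(T > 6)].

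- P(T > 6) = 2^(−6/3.7) = 0.325.
- P(D > 6) = (λ₂e^(−6λ₁) − λ₁e^(−6λ₂)) / (λ₂ − λ₁), with λ₁ = ln 2/3.7 and λ₂ = ln 2 divided by the post-progression median.
- Post-progression median 1.7 months: P(D > 6) = 0.528, difference 0.203, excess 2.0 / 4.1 / 6.1 points.
- Median 3 months: 0.646, difference 0.321, excess 3.2 / 6.4 / 9.6 points.
- Median 10 months: 0.856, difference 0.531, an upper limit of 5.3 / 10.6 / 15.9 points. The true excess is lower because survivors at the cut-off are moved back to their last scan.

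**Simulation** (at least 200,000 participants per scenario). Each cell gives Kaplan-Meier 6-month PFS under 9.4.3 versus clinical progression counted at its own date, in %.

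| Post-progression median | c = 10% | c = 20% | c = 30% |
|---|---|---|---|
| 1.7 months | 37.0 vs 35.0 (+2.0) | 38.7 vs 34.8 (+3.9) | 40.4 vs 34.5 (+5.9) |
| 3 months | 38.2 vs 35.2 (+3.0) | 40.7 vs 34.7 (+6.0) | 43.7 vs 34.7 (+9.0) |
| 10 months | 39.2 vs 35.2 (+4.0) | 42.9 vs 34.7 (+8.2) | 47.1 vs 34.7 (+12.4) |

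**Rescanning.** With a 5-month post-progression median the excess is 3.6 / 7.3 / 11.1 points. If half of the affected participants are scanned at the next slot, it falls to 1.9 / 4.0 / 5.9.

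**Which rule causes it.** At c = 20%, ignoring later deaths and censoring at the last scan gives 42.3-42.4%. The written rule gives 40.7-42.9% (post-progression median 3 to 10 months) and the reference 34.7%. Dropping the deaths leaves the excess in place. Counting clinical progression as an event removes it.

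**New therapy before progression, alone.** At 10% of participants: 35.9-36.1% versus 35.4-35.6%. At 20%: 36.4-37.0% versus 35.3-35.6%. This adds about 0.3 to 1.7 points.

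**The case against.** The strongest reply is that an objective-only PFS is what RECIST 1.1 implies, and that open-label investigator judgment is a softer event. That stands, and it is why the main definition should stay.

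SAP v2.0 holds the PFS definitions and may already contain the missing rules. That also stands and makes the request conditional. It does not remove the gap in Protocol 9.4.3, and SAP v3.0 (Section 6.2) records no change to the protocol's analyses.

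Protocol 7.1 and 10.6.1 ask for every effort to document progression radiologically, and Protocol 8.1 repeats imaging at the end-of-treatment or safety visit if none was done within 12 weeks. This reduces the bias, and the rescanning scenario shows by how much. For scale, the approximate 80% interval half-width at 35% is 1.28 × √(0.35 × 0.65/n): 9 points for n = 45 and 15 for n = 17.

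A reader might infer more than the documents support:
- That GBM/AA is affected in the same way. It is not: RANO PD in Protocol 10.6.3 includes clinical deterioration and failure to return because of death or decline. The open point there is dating. The scan-date rule in 9.4.3 must be reconciled with Protocol 8.1, which dates some progressions at neurological decline, and with 10.6.3.
- That counting late deaths creates the bias. The comparison above shows that it does not.
- That SAP 5.3.2 contradicts 9.4.3. The clinical category is a separate descriptive row, so the two are unaligned rather than contradictory. The sentence in 7.1 stands under treatment withdrawal and does not mention PFS.

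**Conclusion.** The concern holds for the five RECIST cohorts. Under the visible text, clinical progression with no later scan is not a PFS event, the resulting censoring is informative, and PFS and 6-month PFS are biased upward. The direction was the same in every scenario examined.

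The size is conditional. It is about 2-4, 4-8 and 6-12 points in 6-month PFS at 10, 20 and 30% clinical-only progression, and about half that if half are rescanned. It rests on the assumed share, a 3.7-month median to progression, exponential times and a post-progression median of 1.7 to 10 months. Only the trial's own counts can settle it.

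The consequence is limited. PFS is secondary and summarized descriptively, no PFS threshold exists, and the hypotheses and stage boundaries in Protocol 9.1 and 9.2 use ORR alone. This is a cheap improvement to how PFS can be read. It is not a defect in the primary analysis.

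**What to change.** Keep the main PFS definition. Unless SAP v2.0 already provides it, replace the statement in SAP 5.4.1.3 with a sensitivity analysis of PFS and 6-month PFS for each RECIST cohort:

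1. Count investigator-determined clinical progression without radiological PD as an event on its recorded date. If no such date was recorded, use the date of treatment discontinuation for that reason.
2. As a second variant, also count the start of new systemic anti-cancer therapy before documented PD as an event. Keep it separate, because it also captures participants who stopped for toxicity, and its own contribution is small.
3. Report per cohort how many participants each variant affects.

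For GBM/AA, state which date defines progression when RANO PD is clinical, so that 9.4.3, 8.1 and 10.6.3 agree.

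The cost is a short SAP text and one extra Kaplan-Meier table per cohort. Reasons for withdrawal (Protocol 7) and first subsequent therapy (Table 1-2) are recorded. The documents do not name a field for the date of clinical progression in the RECIST cohorts, hence the fallback date. The sensitivity PFS will be somewhat shorter, and its added event depends on open-label judgment, so it belongs beside the main analysis and not in its place.
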